**Lack of Efficacy** – Subject requires alternate treatment for acne after at least 2 weeks of study drug treatment and the risk of continuing the subject in the study outweighs the benefit as determined by the investigator.

**Withdrawal by Parent/Guardian** – An indication that the study participant has been removed from the study by the parent or legal guardian. Consent withdrawal, subject moved, schedule conflicts.

**Study Terminated by Sponsor** – An indication that a clinical study was stopped by its Sponsor.

**Other** – Specify in comments section of final eCRF.

Subjects who terminate treatment early will be asked to complete all Week 12 assessments and procedures prior to commencement of any alternative therapy for acne (if possible). Subjects who discontinue from the study during the treatment period will not be replaced.

All subjects are free to withdraw from participating in this study at any time and for whatever reason, specified or unspecified, and without prejudice. No constraints will be placed on ordinary subject management, and subjects, when appropriate, will be placed on other conventional therapy upon request or whenever clinically necessary as determined by their physician.

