## 12 Statistics

All statistical processing will be performed using SAS® version 9.3 or later unless otherwise stated. Statistical significance will be based on two-tailed tests of the null hypothesis resulting in p-values of 0.05 or less.

The primary method of handling missing efficacy data will be based on estimation using the method of Markov Chain Monte Carlo (MCMC) imputation. This method provides robust estimation when the pattern of missingness is arbitrary. Additionally, the estimation will be done

for each treatment group separately so that the pattern of missingness for one group does not influence the estimation of missing data for another group. Groups of complete datasets following the estimation will be concatenated to form analysis datasets for the comparative analyses and subsequent imputation result inference with SAS PROC MIANALYZE. Descriptive statistics will also be derived from the multiply imputed datasets.

Additionally, a model-based multiple imputation process will be used as a sensitivity analysis to the MCMC imputation. The absolute change in lesion count will also be analyzed using a repeated measures ANCOVA for lesion count data or a repeated measures logistic regression model (generalized estimating equations) for the dichotomized EGSS. Finally, a tipping point analysis will be performed for the primary endpoints.

A statistical analysis plan (SAP), describing all statistical analyses will be provided as a separate document. The SAP will be finalized prior to unblinding of the study treatments.

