**Syntax:**

```
proc mi data=datain out=dataout seed=&seed. nimpute=5<options>;
  where trtpn=(1, or 2);
  mcmc chain=multiple;
  var baseline week2 week4 week8 week12;
  run;
```

2. For each complete data set, the absolute change in lesion counts will be computed. Each complete data set will be analyzed as specified for the particular analysis.
3. The results from these analyses will be combined into a single inference using SAS PROC MIANALYZE.

A total of 4 random seeds will be needed to impute inflammatory lesion counts and non-inflammatory lesion counts for the two treatment groups. Those 4 random seeds have been pre-specified by using a random number generator:

- Inflammatory Lesion Counts; IDP-120 Gel: Seed= 34116691
- Inflammatory Lesion Counts; IDP-120 Vehicle: Seed= 1806432384
- Non-Inflammatory Lesion Counts; IDP-120 Gel: Seed= 2049678471
- Non-Inflammatory Lesion Counts; IDP-120 Vehicle: Seed= 655282615

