### 12.1.10 Sensitivity Efficacy Analyses

#### Sensitivity analyses for absolute change in lesion count

The first sensitivity analysis for absolute change in lesion count will use a repeated measures ANCOVA, with treatment, analysis center, and visit (ie, Week 4, Week 8) as independent factors and a covariate of baseline lesion count. In this analysis, data from all post-baseline visits will be included with no imputation for missing data.

The second sensitivity analysis will use the model based multiple imputation method to impute missing data for the absolute change in lesion counts at Week 12. Although the full details will be presented in the SAP, the multiple imputation will involve 3 principal tasks:

1. Missing values will be filled in 5 times to generate 5 data sets. The imputation model used will be an ANCOVA with factors of treatment group and analysis center, and a covariate of baseline lesion count (ie, the imputation model will be the same as the analysis model). Appropriate modifications will be made should the analysis be based on a non-parametric method.
2. Each complete data set will be analyzed with an ANCOVA with factors of treatment group, and analysis center, and a covariate of baseline lesion count.
3. Results from these analyses will be combined into a single inference using SAS PROC MIANALYZE.

A total of 2 random seeds will be needed. Those 2 random seeds have been pre-specified by using a random number generator:

- Inflammatory Lesion Counts: Seed= 1792696133
- Non-Inflammatory Lesion Counts: Seed= 1438330601

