#### Sensitivity analyses for EGSS

The first sensitivity analysis for the dichotomized EGSS success will use a repeated measures logistic regression model (generalized estimating equations), with dichotomized EGSS success as the dependent variable and treatment, analysis center, and visit (ie, Week 4, Week 8) as independent factors. In this analysis, data from all post-baseline visits will be included with no imputation for missing data.

The second sensitivity analysis will use the model based multiple imputation method to impute missing data for the dichotomized EGSS data. Although the full details will be presented in the SAP, the multiple imputation will involve 3 principal tasks:

1. Missing values will be filled in 5 times to generate 5 data sets. The imputation model used logistic regression with factors of treatment group and analysis center (ie, the imputation model will be the same as the analysis model).
2. Each complete data set will be analyzed with a logistic regression a factors of treatment group and analysis center.
3. Results from these analyses will be combined into a single inference using SAS PROC MIANALYZE.

A total of 1 random seed will be needed. The random seed has been pre-specified by using a random number generator:

- EGSS: Seed= 461039866

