#### Tipping Point Analysis

A tipping point analysis of each primary endpoint will be performed as a sensitivity analysis for the handling of missing data.

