### **12.8.6 Windowing Rules**

The timing of all study visits is relative to Baseline (Day 0). The Week 2, Week 4 and Week 8 visits should occur within  $\pm$  3 days of the scheduled times, the Week 12 visit should occur within -3 / +5 days of the scheduled time.

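### As specified, the second sensitivity analysis (parametric lesion counts and EGSS) returns the observed-Week-12 estimate plus noise and leaves Week 2, 4 and 8 data unused

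*Combined protocol and SAP*

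**What the plan says.** Section 12 states that "a model-based multiple imputation process will be used as a sensitivity analysis to the MCMC imputation". Section 12.1.10 gives the models.

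- **Lesion counts.** The Week 12 absolute change is imputed five times, from an ANCOVA with treatment, analysis center and a "covariate of baseline lesion count (ie, the imputation model will be the same as the analysis model"). Each completed data set is then analysed with that ANCOVA.
- **EGSS.** The dichotomized outcome is imputed by "logistic regression with factors of treatment group and analysis center (ie, the imputation model will be the same as the analysis model"), and the same logistic model is refitted.

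The primary imputation in Section 12.1.9 is run separately by arm, for lesion counts and for EGSS, with the variable list "var baseline week2 week4 week8 week12". Analysis center is not in that list.

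Section 12.1.10 also plans a repeated-measures ANCOVA or GEE on all post-baseline visits without imputation. On missing data it adds: "A tipping point analysis of each primary endpoint will be performed as a sensitivity analysis for the handling of missing data". It leaves further detail of the second analysis to the SAP and leaves the adaptation to a rank-based analysis open.

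**The concern.** A sensitivity analysis for missing data should change the assumption or the method in a way that can be interpreted. Here the imputation step changes nothing systematic. The result is an ANCOVA or logistic regression on subjects with an observed Week 12 value, presented as multiple imputation.

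Subjects who miss Week 12 after attending Weeks 2, 4 or 8 contribute none of those data, although the primary imputation uses them. If leaving depends on earlier response, the planned estimate can move away from the truth while the primary does not. A reader who takes both as full imputation analyses could misread a gap between them, or their agreement.

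**Working it through.** **1. Models side by side** (Sections 12.1.9 and 12.1.10; five imputations in each)

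| Term | Primary imputation | Planned, lesions | Planned, EGSS |
|---|---|---|---|
| Treatment | separate by arm | factor | factor |
| Baseline value | yes | yes | no |
| Weeks 2, 4, 8 | yes | no | no |
| Analysis center | no | yes | yes |
| Form | normal (EGSS rounded) | ANCOVA | logistic |

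Neither predictor set contains the other.

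**2. Why the estimate is unchanged.** Let o and m index observed and missing Week 12 values, X the analysis-model terms and b the fit to observed data, so X_o'(y_o − X_o b) = 0. An imputed value is y* = X_m(b + d) + e, where d and e are random draws with mean zero. Refitting the same model gives

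b_completed = b + (X'X)⁻¹ X_m'(X_m d + e).

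The second term has mean zero whatever the dropout mechanism. The pooled estimate is therefore b plus noise that shrinks as imputations are added. For the logistic model the same holds approximately, through the score equation.

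**3. Plan figures used as inputs.** The plan states no figure for this analysis. Section 12.8.2 gives 13.3 − 8.7 = 4.6 with SD 11.0 and 300 per arm, and its power claim reproduces: 4.6 / (11.0 × √(2/300)) = 5.12, and Φ(5.12 − 1.96) = 0.999, above the stated 99%. Both lesion paragraphs there are labelled non-inflammatory; I take this first one as inflammatory. EGSS success of 26.6% against 14.3% gives a log odds ratio of ln[(0.266/0.734)/(0.143/0.857)] = 0.78.

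**4. Equivalence in simulation** (300 per arm, only Week 12 missing)

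- Lesions: the mean of planned minus observed-Week-12 estimate was within 0.03 lesions in every scenario. The SD was 0.13 to 0.23 with 5 imputations. In the set run with 200 imputations it was 0.02 to 0.03.
- The standard error was no smaller than from the direct fit: 0.936 against 0.927 at 11% missing, and 0.991 against 0.968 at 20%.
- EGSS at 15% missing: mean difference in log odds ratio 0.002, SD 0.044.

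**5. Bias when dropout depends on Week 8.** Entries are estimate minus full-data estimate, in lesions; negative means the benefit is understated. Rates and mechanisms are assumed. Set 1 has 25 centers. Set 2 has 30 centers, Week 8 to Week 12 correlation 0.8 and dropout log odds of 1.2 per SD of Week 8 change. Set 2 entries are for the observed-Week-12 fit, which the planned result matched within 0.01.

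| Dropout rule | Set 1, 10%/20% missing | Set 2 |
|---|---|---|
| Same rule, both arms | −0.19 / −0.33 | 4.381 − 4.618 = −0.24 (11%); 4.244 − 4.589 = −0.35 (20%) |
| Vehicle only | −0.85 / −1.57 | 3.452 − 4.536 = −1.08 (10%); 2.785 − 4.626 = −1.84 (18%) |

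Adding Week 8 to the imputation in set 2 brought the estimate within 0.02 of full data in all four cases. The direction is not fixed. In a further set (correlation 0.7, dropout tied to the Week 8 residual), planned minus primary-type imputation was −0.69/−1.35 for vehicle-only dropout and +0.70/+1.36 for active-only. For EGSS with vehicle-only dropout (20 centers, log odds 1 per grade), the log odds ratio was 0.73/0.64 planned and 0.81/0.80 primary-type, against about 0.80 with full data.

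**6. Where the planned model does better.** With dropout that depends on center, opposite by arm, the primary-type imputation was off by −0.16/−0.26. In a similar set (center SD 4) it was off by −0.17/−0.28, while the planned model was off by 0.00/−0.02.

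**7. Both predictor sets together.** A model with Weeks 2, 4 and 8, treatment-by-visit terms and center stayed within 0.02 lesions of full data in the vehicle-only case of step 5 (set 1) and the center case of step 6.

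**The case against.** The strongest reply is that the planned analysis is a legitimate contrast. It conditions on center, which the primary imputation omits, and step 6 shows it can be right where the primary is off. A gap from the primary can also signal arm-differential dropout linked to early response. Both points stand. They are reasons to keep center and to keep an observed-Week-12 analysis under its proper name; they do not justify an imputation step that adds only noise.

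Other analyses cover part of the ground: the repeated-measures and GEE models use all visits, and the tipping point analysis covers each primary endpoint. That is why the consequence is limited. As listed, though, the repeated-measures models have no treatment-by-visit term, so they do not isolate Week 12.

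Deferral to the SAP does not answer the point, because Section 12.1.10 already equates the imputation terms with the analysis terms and nothing supplied adds a predictor. The rank version is open, so the lesion-count half applies only if the parametric analysis is used.

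Four further readings are tempting and are not supported:

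- **That the planned assumption is stricter than the primary's.** The two are not nested (step 1).
- **That bias vanishes if both arms drop out by the same rule.** A common rule on actual Week 8 response still gave −0.19/−0.33. A zero arises only if dropout is tied to the within-arm residual at equal rates.
- **That agreement hiding missing-not-at-random dropout is a fault of this analysis.** That limit applies to any pair of missing-at-random analyses, including the revised one.
- **That this is a completers analysis.** Section 8.3 says "Subjects who terminate treatment early will be asked to complete all Week 12 assessments and procedures prior to commencement of any alternative therapy". Whether such values count as Week 12 is a separate question, which also touches the primary analysis.

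**Conclusion.** The point holds for the parametric lesion-count analysis and for EGSS. The equivalence with the observed-Week-12 estimate is algebraic for the ANCOVA, approximate for the logistic model, and needs no dropout assumption. A single run with five imputations will differ from the direct fit by noise of about 0.13 to 0.23 inflammatory lesions (SD).

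The bias sizes do rest on assumptions, because the documents give no dropout rate, mechanism or visit correlations. With 10% to 20% missing and a true difference of 4.6, the simulated understatement ran from about 0.2 to 0.35 lesions under a common Week 8 rule and from about 0.85 to 1.8 with vehicle-only dropout. The sign reverses if the selective dropout is on active.

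A reader might infer that a co-primary conclusion is at risk. It is not: no co-primary decision rests on this analysis, and the primary, repeated-measures/GEE and tipping point analyses are unaffected. The change should be made because it is cheap and gives the analysis a clear purpose.

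**What to change.** In the SAP, before unblinding:

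1. Add the observed Week 2, 4 and 8 values, with treatment-by-visit terms, to the imputation model and keep analysis center. For EGSS also add baseline grade and keep the logistic form.
2. Use one EGSS model across arms. With 25 centers there are 300/25 = 12 vehicle subjects per center, and at 14.3% success 0.857¹² = 0.157, so about 16% of such centers would have no vehicle success to support a by-arm model with center.
3. Say how missing earlier visits are filled, since a subject who leaves before Week 8 lacks that predictor too.
4. To keep the diagnostic contrast, fit the ANCOVA and logistic model directly to observed Week 12 data and label the result an observed-Week-12 analysis.

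The revised model then holds the predictors of both imputations. It checks the primary's omission of center and, for EGSS, its rounded normal method.

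The cost is SAP wording, minor reprogramming and one extra table, using data already collected. The revised imputation will usually lie close to the primary and still assumes missing at random, so the tipping point analysis must carry departures from that assumption.

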#### Sensitivity analyses for EGSS

The first sensitivity analysis for the dichotomized EGSS success will use a repeated measures logistic regression model (generalized estimating equations), with dichotomized EGSS success as the dependent variable and treatment, analysis center, and visit (ie, Week 4, Week 8) as independent factors. In this analysis, data from all post-baseline visits will be included with no imputation for missing data.

The second sensitivity analysis will use the model based multiple imputation method to impute missing data for the dichotomized EGSS data. Although the full details will be presented in the SAP, the multiple imputation will involve 3 principal tasks:

1. Missing values will be filled in 5 times to generate 5 data sets. The imputation model used logistic regression with factors of treatment group and analysis center (ie, the imputation model will be the same as the analysis model).
2. Each complete data set will be analyzed with a logistic regression a factors of treatment group and analysis center.
3. Results from these analyses will be combined into a single inference using SAS PROC MIANALYZE.

A total of 1 random seed will be needed. The random seed has been pre-specified by using a random number generator:

- EGSS: Seed= 461039866

#### Tipping Point Analysis

A tipping point analysis of each primary endpoint will be performed as a sensitivity analysis for the handling of missing data.

#### **12.1.11 Subgroup Analyses**

Subset analyses will be conducted for the ITT populations for the subgroups of baseline global severity, gender, age, ethnicity, and race. Age will be dichotomized to less than the median age of subjects and greater than or equal to the median age of subjects. An additional analysis will include age with categories of less than 18 and greater than or equal to 18. Subset analyses will be conducted on the variables absolute change from baseline in inflammatory lesions and non-inflammatory lesions at Week 12 as well as the dichotomized global severity score at Week 12. These analyses will contain only descriptive statistics.

### **12.1.12 Subject Self-Assessments**

Subjects will be asked to complete the Acne-Specific Quality of Life Questionnaire (Appendix 17.3). Descriptive statistics will be used to summarize the data reported for the questionnaire. No inferential analyses will be conducted.

## **12.2 Assessment of Safety**

Safety will be evaluated by tabulations of adverse events (AEs), Cutaneous Safety Evaluation, and Tolerability Evaluations. Cutaneous Safety Evaluation scores (erythema, scaling, and hypo/hyper-pigmentation) and Tolerability (itching, burning, and stinging) will be presented with descriptive statistics at Baseline and at Weeks 2, 4, 8, and 12 for each treatment group.

Frequencies and percentages for each outcome category will be included in these statistics. Mean values will be presented graphically by week and treatment group.

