**Safety Evaluation:**

All subjects who are confirmed to have used the study drug at least once will constitute the safety population. Safety will be evaluated by tabulations of adverse events (AEs), Cutaneous Tolerability Evaluations, vital signs/abbreviated physical exams, and safety labs.

Cutaneous Safety Evaluation scores (erythema, scaling, and hypo/hyper-pigmentation) and Tolerability (itching, burning, and stinging) will be presented with descriptive statistics at Baseline and at Weeks 2, 4, 8, and 12 for each treatment group. Frequencies and percentages for each outcome category will be included in these statistics. Mean values will be presented graphically by week and treatment group.

Vital signs, an abbreviated physical exam, and safety labs will be conducted on all subjects at specified visits. For pre-menses females and females of child-bearing potential (FOCBP), urine pregnancy testing and serum pregnancy testing will occur at specified visits. Changes from baseline in safety laboratory values and vital sign measurements will be summarized with descriptive statistics for each treatment group at all applicable study visits. Shift tables will be presented for changes in safety laboratory values collected at Baseline and Week 12 Visits. Normal ranges established by the central laboratory will be used to determine the shifts. A listing of all out-of-range laboratory test results at any assessment time point will also be provided.

Determination of clinical significance for all out-of-range laboratory values will be made by each investigator and included in the listing. In addition, a listing of all clinically significant laboratory test results will be provided.

All recorded prior and concomitant medications will be classified based on terminology from the WHO Drug Dictionary. Therapies and medications data will be presented in the data listings.

All adverse events occurring during the study will be recorded and classified on the basis of MedDRA terminology. Descriptions of AEs will include the date of onset, the date the AE ended, the severity of the AE, the relationship to study drug, the action taken regarding study drug usage, the action taken regarding to treat the AE, and the outcome. Adverse events will be summarized by treatment group and severity. Each subject will be counted only once within a system organ class or a preferred term by using the adverse events with the highest severity within each category.

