**Table 1. Study Design and Schedule of Assessments**

PROCEDURES	VISIT 1  Screening Visit Day -35 to 0	VISIT 2 Baseline Day 0	VISIT 3 Week 2 (Day 14 ±3 days)	VISIT 4 Week 4 (Day 28 ±3 days)	VISIT 5 Week 8 (Day 56 ± 3 days)	VISIT 6  Week 12 (Day 84 -3/+5 days)
Informed consent/Accent	X					
Obtain Subject Number from IWRS	X					
Demographics	X					
Medical history 	X	X				
Inclusion/Exclusion criteria 	X	X				
Previous therapies 	X	X				
Acne-QoL		X				X
Pregnancy Test (pre-menses & FOCBP) 	X	X	X	X	X	X
Abbreviated physical examination 		X				X
Vital sign measurements		X				X
Safety labs (CBC/diff, serum chemistry)		X				X
EGSS	X	X	X	X	X	X
Lesion Counts	X	X	X	X	X	X
Photographs (select sites only)		X	X	X	X	X
Cutaneous Safety Evaluation		X	X	X	X	X
Tolerability Evaluation		X	X	X	X	X
Randomization in IWRS (obtain kit #)		X		X	X	
Administer Subject Instructions (Appendix 17.1)		X				
Dispense Study Drug (one IWRS-assigned pump)		X		X	X	
Weigh Study Drug to the nearest 0.1gram		X	X	X	X	X
Study Drug applied at investigational center		X	X	X	X	
Study Drug Collected				X	X	X
Subject Diary Calendar dispensed		X	X	X	X	
Subject Compliance Reviewed / Diary			X	X	X	X
Adverse Events	X	X	X	X	X	X
Concomitant Therapy and Prohibited Therapies Review	X	X	X	X	X	X
End of Study						X

 If no washout is needed, Visits 1 and 2 may occur on the same day. If a washout is needed, Visit 2 must occur after the appropriate washout period.

 Update at baseline visit prior to randomization.

 Height will be measured at baseline only; weight measurements and examinations of other abbreviated physical parameters will be performed at Baseline and Week 12.

 For pre-menses females and FOCBP, the urine pregnancy test must be completed at all scheduled visits, as per schedule. Serum pregnancy testing will be completed at Baseline and Week 12 only. Subjects with a positive pregnancy test at any time during the study will be discontinued.

 All Week 12 procedures should be completed for all subjects who terminate early.

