### 11.3.1 Cutaneous Safety Evaluations

Cutaneous safety will be evaluated through assessment of scaling, erythema, hypo-pigmentation and hyper-pigmentation at the drug-application site at the time of the visit. Cutaneous tolerability will be evaluated through assessment of selected local signs and symptoms at the drug-application site: itching, burning and stinging, as an average since the last visit.

Cutaneous safety and tolerability signs and symptoms that result in the subject requiring a concomitant therapy, interruption of treatment, or discontinuation from the study, will be reported as an AE.

(Note: To be assessed by the evaluator at the time of the study visit.)

*Scaling:*

0 – None	No scaling
1 – Mild	Barely perceptible, fine scales present on limited areas of the face
2 – Moderate	Fine scale generalized to all areas of the face
3 – Severe	Scaling and peeling of skin over all areas of the face

*Erythema:*

0 – None	No evidence of erythema present
1 – Mild	Slight pink coloration
2 – Moderate	Definite redness
3 – Severe	Marked erythema, bright red to dusky dark red in color

*Hypo-pigmentation:*

0 – None	No evidence
1 – Mild	Slight, barely perceptible
2 – Moderate	Definite, evident
3 – Severe	Marked, prominent

*Hyper-pigmentation:*

0 – None	No evidence
1 – Mild	Slight, barely perceptible
2 – Moderate	Definite, evident
3 – Severe	Marked, prominent

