### 11.3.2 Tolerability Evaluations

To be reviewed with the subject at the study visit as average over the period since the previous visit.

*Itching:*

0 – None	No itching
1 – Mild	Slight itching, not really bothersome
2 – Moderate	Definite itching that is somewhat bothersome
3 – Severe	Intense itching that may interrupt daily activities and/or sleep

*Burning:*

0 – None	No burning
1 – Mild	Slight burning sensation; not really bothersome
2 – Moderate	Definite warm, burning sensation that is somewhat bothersome

3 – Severe Hot burning sensation that causes definite discomfort and may interrupt daily activities and/or sleep

*Stinging:*

0 – None	No stinging
1 – Mild	Slight stinging sensation, not really bothersome
2 – Moderate	Definite stinging sensation that is somewhat bothersome
3 – Severe	Stinging sensation that causes definite discomfort and may interrupt daily activities and/or sleep

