### **12.2.1 Adverse Events**

All AEs occurring during the study will be recorded and classified on the basis of MedDRA terminology. Descriptions of AEs will include the date of onset, the date the AE ended, the severity of the AE, the relationship to study drug, the action taken regarding study drug usage, the action taken to treat the AE, and the outcome. All reported treatment-emergent AEs (TEAEs) will be summarized by the number of Subjects reporting AEs, system organ class, preferred term, severity, seriousness, and relationship to study drug. TEAEs are those AEs with an onset on or after the date of the first study drug application.

Adverse events will be summarized by treatment group and severity. Each subject will be counted only once within a system organ class or a preferred term by using the adverse events with the highest severity within each category.

Adverse events will be summarized by treatment group and relationship to study drug. Each subject will be counted only once within a system organ class or a preferred term by using the adverse events with the greatest relationship within each category.

Comparisons among treatment groups will be made by tabulating the frequency of subjects with one or more AEs (classified into MedDRA terms) during the study. The Fisher's Exact test will be used to compare the percentage of subjects in each treatment group who report any adverse event at a significance level of 0.05. The specific system organ classes and preferred terms analyzed will be those that are reported by at least one percent of the subjects in any treatment group.

All information pertaining to AEs noted during the study will be listed by subject, detailing verbatim given by the investigator, preferred term, system organ class, start date, stop date, severity, actions taken, and drug relatedness. The AE onset will also be shown relative (in number of days) to the day of initial dose of the randomized study drug.

Serious adverse events (SAEs) will be tabulated by subject within treatment groups.

In addition, a list of subjects who discontinued from the study and a list of subjects who experienced SAEs will also be provided.

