### **12.2.2 Safety Laboratory Tests**

Changes from baseline in safety laboratory values will be summarized with descriptive statistics at all applicable study visits. Shift tables will be presented for changes in safety laboratory values. Normal ranges established by the central laboratory will be used to determine the shifts. A listing of all out-of-range laboratory test results at any assessment time point will also be provided. Determination of clinical significance for all out-of-range laboratory values will be made by each investigator and included in the listing. In addition, a listing of all clinically significant laboratory test results will be provided.

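### The planned tolerability tables run visit by visit only, so they cannot show how many subjects per arm ever had a moderate or severe local reaction score.

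*Combined protocol and SAP*

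**What the plan says.** Both the synopsis objective and Section 6 name tolerability in the primary objective. Sections 11.3.1 and 11.3.2 define seven four-point scales, each scored 0 to 3: scaling, erythema, hypo-pigmentation, hyper-pigmentation, itching, burning and stinging.

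For their analysis, Section 12.2 says that the scores "will be presented with descriptive statistics at Baseline and at Weeks 2, 4, 8, and 12 for each treatment group" and adds that "Frequencies and percentages for each outcome category will be included in these statistics". The synopsis (Safety Evaluation) repeats this and adds "Mean values will be presented graphically by week and treatment group". No other summary of these scales appears in the protocol text.

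Other safety data are treated differently. For laboratory data, "Shift tables will be presented for changes in safety laboratory values" (Section 12.2.2). For adverse events, "Each subject will be counted only once within a system organ class or a preferred term by using the adverse events with the highest severity" (Section 12.2.1), which is a cumulative, worst-grade count.

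Three further provisions matter here:

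- Section 11.3.1, on local reactions: those "that result in the subject requiring a concomitant therapy, interruption of treatment, or discontinuation from the study, will be reported as an AE".
- Table 1, footnote 5: "All Week 12 procedures should be completed for all subjects who terminate early". Those procedures include the cutaneous scales. Section 12.8.6 gives windows for scheduled visits only and does not say which analysis visit an early-termination score belongs to.
- Section 11.3.2, on itching, burning and stinging: "To be reviewed with the subject at the study visit as average over the period since the previous visit".

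**The concern.** A reader of a topical retinoid and benzoyl peroxide trial wants to know what share of subjects had at least moderate irritation at some point on treatment. The planned tables answer a different question, namely what share had it at each visit. Transient reactions that strike different subjects at different visits leave every visit percentage low while the cumulative share is much higher. If the same subjects are affected throughout, the cumulative share equals the highest visit percentage. The planned tables look the same in both cases.

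At stake is the trial's main descriptive statement on local tolerability. The highest entry in a by-visit table is likely to be quoted as the irritation rate, although it is only the lowest value that the cumulative rate can take. No efficacy test is affected.

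**Working it through.** **Plan's own figure.** None. The documents state no expected tolerability rate, so every rate below is an assumption. The 300 per arm is from Section 12.8.2 and only converts percentages to counts.

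**Step 1: what visit percentages determine.** Let p1 to p4 be the proportions moderate or severe at Weeks 2, 4, 8 and 12 in one arm with complete data. The proportion ever affected, E, satisfies

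max(p1, ..., p4) ≤ E ≤ p1 + p2 + p3 + p4.

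The lower bound holds when every affected subject is among those affected at the worst visit. The upper bound holds when no subject is affected twice. If visits were independent, E = 1 − (1−p1)(1−p2)(1−p3)(1−p4).

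**Step 2: falling rates of 10%, 8%, 5% and 3%.**

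- Lower bound: 10%, or 30 of 300.
- Upper bound: 10 + 8 + 5 + 3 = 26%, or 78 of 300.
- Independence: 1 − 0.90 × 0.92 × 0.95 × 0.97 = 23.7%.

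With a latent normal model, equal correlation between all pairs of visits and thresholds set to give these visit rates:

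| Correlation | Ever affected |
|---|---|
| 0.2 | 21.9% |
| 0.5 | 18.6% |
| 0.8 | 14.3% |

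The highest entry in the planned tables is 10% in every row.

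**Step 3: other assumed rates, 300 per arm.**

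| Rate at the four visits | Lower bound | Independence | Upper bound |
|---|---|---|---|
| 3% each | 3% (9) | 11.5% | 12% (36) |
| 5% each | 5% (15) | 18.6% | 20% (60) |
| 10% each | 10% (30) | 34.4% | 40% (120) |
| 10/8/4/2% | 10% (30) | 22.1% | 24% (72) |

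**Step 4: can the adverse event tables supply the count?** Section 11.3.1 makes a reaction a mandatory adverse event when it leads to concomitant therapy, interruption or discontinuation. A severe score endured without any of these is not covered by that rule. Severity is also graded differently. Section 11.4.4 grades by treatment needed and effect on daily activities. The scales in 11.3.1 grade by appearance, such as colour or extent of scale, and those in 11.3.2 by how bothersome the sensation is. A moderate or severe adverse event is therefore not the same as a score of 2 or 3.

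**Step 5: does dropout distort the time course?** Keep the Step 2 rates and assume that 30% of those affected at Week 2 stop and are absent later. The rate displayed at a later visit j is

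(pj − 0.3 × P(affected at both Week 2 and visit j)) / (1 − 0.3 × 0.10).

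Across correlations of 0.2 to 0.8, Week 4 shows 7.8% to 6.7% instead of 8%, and Week 12 shows 2.9% to 2.4% instead of 3%. The assumed fall from Week 2 to Week 12 is 7 percentage points. Dropout adds about 0.1 to 0.6.

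**The case against.** By-visit tables are an accepted way to show tolerability over time, and the scores are held per subject, so a worst-score count can be produced at any time without new data. Section 11.4.1 defines adverse events broadly and 11.4.2 has all of them recorded. Section 11.3.1 says which reactions must be reported as adverse events, not that others may not be. Many moderate or severe reactions may therefore reach the cumulative adverse event tables. Section 12 also defers full detail to a separate SAP, which is not part of the text available here and might contain the table.

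Much of this stands, and it rules out three stronger readings that a reader might draw:

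- *The trial cannot state the cumulative figure.* It can. The limit lies in the planned tables. A count added after unblinding would, however, be post hoc.
- *Subjects who quit because of irritation vanish.* They do not. Discontinuation makes the reaction a reportable adverse event, which enters the once-per-subject table in 12.2.1, and Section 12.3 tabulates reasons for discontinuation. Their final scores are to be collected. Whether those scores enter a later visit column is unspecified. Summing the category frequencies also reveals the number assessed at each visit.
- *Much of any decline in irritation is dropout.* On the assumed inputs, Step 5 shows a small effect. Nothing in the documents shows that such dropout would be greater on active gel.

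The objection does not show that any planned table gives the number ever moderate or severe on the protocol's own scales.

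**Conclusion.** The point holds for the planned tables. On the assumed rates of 10/8/5/3%, they show at most 10% where the cumulative proportion may be anything from 10% to 26%, and about 14% to 22% for correlations of 0.8 to 0.2. The bounds assume complete data at four visits. The narrower range also assumes the latent normal model. The adverse event tables do not close the gap, because their trigger and severity scale differ.

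The missing rule for early-termination scores and the unstated visit denominators are gaps in detail, worth closing in the same edit. The conclusion rests on the protocol text alone. A separate SAP that adds a worst-score table would settle it.

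One limit remains whatever is tabulated: itching, burning and stinging are averages since the last visit, so the worst recorded score is not the peak.

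**What to change.** In Section 12.2, before unblinding:

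1. For each scale and arm, tabulate each subject's worst post-baseline score, including early-termination scores, with the number and percentage moderate or severe.
2. Add a baseline-to-worst shift table for each scale.
3. Use as denominator the safety population with at least one post-baseline assessment.
4. Keep the by-visit tables and mean plots, and print the number assessed at each visit.
5. State in 12.8.6 that an early-termination score does not enter the Week 12 column unless it falls in that visit's window (Day 84, −3/+5 days).
6. Add a footnote that the worst itching, burning or stinging score is the worst of averages over the interval between visits.

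The cost is one extra table per scale, seven in all, from data already collected, with no change to visits or sample size. The headline irritation figure will be less favourable, since the worst-score percentage cannot be lower than the highest visit percentage when both use the same subjects.
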